4.1 Study Procedures

All procedures described below (see schedule of events on the next page for overview) will be done for research purposes and are not part of standard clinical care.

A) Initial Contact and Phone screening (Phone, email, in person) (20-30 minutes)

All potential subjects will first come into contact with a research team member via phone, email, or in person. Either the potential subject will contact the research team member of his or her own accord, or the research team member will initiate first contact. Team members will initiate first contact only if the subject has previously signed a document (such as consent form) agreeing to be re-contacted. At this time, the potential subject will be told what the experiment generally involves, including time commitment and compensation.

All subjects who are interested in participating in the study will be asked a series of initial screening questions to determine initial eligibility (see attached phone screen), including questions about physical and mental health and MRI safety. Verbal consent is obtained prior to asking questions on the phone screen (see introduction in phone screen). The Sensory Phenomena Scale (SPS) may also be administered during the phone screen to

determine whether patients' sensory symptoms are severe enough to be eligible for the protocol. Participants who encounter our BuildClinical advertising may elect to answer screening questions prior to the phone screen with a member of the research team. These questions are not a substitute for a comprehensive eligibility screening, and only ask about broader inclusion/exclusion criteria in significantly less detail. If a subject meets eligibility recruitments based upon the phone screen, they will be scheduled for a screening visit on Webex or in-person at the NYU Langone Medical Center with a psychiatric evaluation and medical screening will be conducted. If the subject declines participation, the phone screening questionnaire will be destroyed and no protected health identifiers for the potential subject will be retained.

Schedule of Events:

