- 2. Psychiatric and Symptom Evaluation (90-180 minutes): If consent is acquired, we will perform a longer screening for psychiatric history using the Mini International Neuropsychiatric Interview (M.I.N.I., Sheehan et al. 1998). This tool contains diagnostic modules for the assessment of several psychiatric conditions including mood, substance use, anxiety, psychotic, and eating disorders. The Columbia-Suicide Severity Rating Scale (C-SSRS; Posner et al., 2011) will be used to determine risk for suicide. Sensory phenomena will be assessed using the Sensory Phenomena Scale (SPS, Rosario et al., 2009). This semi-structured scale assesses the presence and severity of different types of SP preceding or occurring at the same times as repetitive behaviors in OCD. The SPS contains a checklist with examples of different types of SP encompassing all previous descriptions in the literature, including physical sensations, "just right" sensations, incompleteness, general energy or inner tension buildup, and urges. OC symptoms in OCD patients will be assessed using the Yale-Brown Obsessive Compulsive Scale (Y-BOCS, Goodman et al., 1989), while tics symptoms in TD patients will be assessed using Yale Global Tic Severity Scale (YGTSS, Leckman et al., 1989). Psychiatric symptoms including suicidality will be confirmed by a licensed clinician on the protocol to ensure participant safety. If the clinician determines that the subject is at an immediate and significant health risk, they will be sent to the nearest Emergency Department. If the visit is conduted remotely via videoconferencing and no study clinician is available at that moment to speak with the participant, a member of the study team will direct the participant to call 911 or go to the nearest psychiatric emergency department. We will also have subjects complete several self-rated scales or questionnaires to assess a variety of other symptoms: Beck Depression and Anxiety Inventories (Beck et al. 1996), Dimensional Obsessive-Compulsive Scale (Abramowitz et al. 2010), Penn State Worry Questionnaire (Meyer et al. 1990), Multidimensional Assessment of Interoceptive Awareness (Mehling et al., 2012), Adolescent/Adult Sensory Profile Scale (Brown and Dunn., 2002), the Perseverative Thinking Questionnaire (PTQ; Ehring et al., 2011), Frost Multidimensional Perfectionism scale (Frost et al., 1990), Obsessive-Compulsive Trait Core Dimensions Questionnaire (Pietrefesa et al., 2009), Resilience Scale (Wagnild et al., 1993), Not Just Right Experiences Questionnaire, Revised (Coles et al., 2003), Obsessive-Compulsive Inventory (Foa et al., 1998), Quick Inventory of Depressive Symptomatology (Rush et al., 2003).

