The experimenter will review the patient's current symptoms (using Y-BOCS/YGTSS, SPS and PRISE) to determine if there have been any changes since the Screening Visit, and explain the cognitive tasks with them. An MRI safety screen will be performed to ensure that the individual is safe to enter the scanning environment.

3. Practice trials on task/pre-task ratings of stimuli (optional, 10-20 minutes)
Participants may be asked to perform practice trials of the task or answer questions about task stimuli.

4. MRI set up and scanning (90 minutes)

When it is time for subjects to be set up in the MRI scanner, they will be introduced to the MRI technician, who will prepare them. The technician is highly trained in participant safety protocols. The technician will run through a checklist with the subject to ensure that no metal objects are on the subject's body. Once cleared, the technician will set up the subject in the scanner and make sure they are comfortable and ready to begin the experiment.

4.a. Eye tracking and Physiological measurements (e.g., respiratory rate, pulse oximetry) may be taken while subjects perform the task inside the scanner. All physiological measurements are non-invasive (e.g., pulse is measured by attachment of device to finger). During the set-up of physiological equipment, participants will be asked to confirm that they are comfortable with the attachments. If they are not comfortable after or during the set-up: 1) the placement will be altered to achieve comfort, or 2) the equipment will be removed. Subjects will never be required to wear the equipment if they are uncomfortable. Physiological measurements will be collected with commercially available BIOPAC equipment.

4.b. MRI scanning

The MRI scanning session will be no more than 90 minutes in total and may include a resting-state fMRI scan (subjects fixate on a crosshair with eyes open, 10 min), 3-4 brief fMRI tasks (35-45 min), diffusion-weighted MRI (10-15 min), and a structural T1-weighted scan (5-10 min).

This may include the following tasks:

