Relationships with clinical symptoms: Testing for Hypothesis 3a: A change score will be computed between SPS score at baseline and after 4 weeks for each subject. Two-sample t-tests will compare ondansetron and placebo groups on SPS change scores to determine whether the intervention reduces SP significantly more than placebo. In addition, change scores from baseline to week 4 will be computed for measures of overall symptom severity (using Y-BOCS and YGTSS) and compared between ondansetron and placebo groups. If there are baseline differences between the groups in any of the symptom scales (SPS, Y-BOCS, or YGTSS), follow-up one-way ANOVAs will compare change scores between ondansetron and placebo groups after adjusting for baseline scores. Testing for Hypothesis 3b: If there are significant differences between ondansetron and placebo groups in (1) SPS change scores and (2) Y-BOCS or YGTSS change scores, a Sobel test of mediation 205, 206 will investigate whether group differences in Y-BOCS/YGTSS changes are mediated by SPS changes. Briefly, mediation analyses perform a series of regressions in order to determine whether the relationship between an independent and dependent variable (e.g., treatment group and Y-BOCS/YGTSS scores) reduces significantly after including a third mediator variable (e.g., SPS score). Testing for Hypothesis 3c: If there are significant differences between ondansetron and placebo groups in (1) SPS change scores and (2) change in ROI activation or connectivity from baseline to week 4, a Sobel test will investigate whether group differences in SPS change are mediated by changes in activation or connectivity.

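### SPS, Y-BOCS and YGTSS are each rated twice before the first dose, but the Hypothesis 3a comparison uses only one rating; entering both as covariates would recover some precision at little cost.

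*Combined protocol and SAP*

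**What the plan says.** All references are to the combined protocol and SAP.

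- **Section 4.1, Screening Visit.** "Sensory phenomena will be assessed using the Sensory Phenomena Scale". By diagnosis, "OC symptoms in OCD patients will be assessed using the Yale-Brown Obsessive Compulsive Scale", and "tics symptoms in TD patients will be assessed using Yale Global Tic Severity Scale".
- **Section 4.1, Baseline Visit (Day 0).** The experimenter goes over symptoms again, "using Y-BOCS/YGTSS, SPS and PRISE) to determine if there have been any changes since the Screening Visit". Study drug is handed out at the end of this visit. The first dose is due the next morning, with up to three days allowed.
- **Section 4.1, phone screen.** A further SPS rating is optional: "The Sensory Phenomena Scale (SPS) may also be administered during the phone screen".
- **Section 4.2, Hypothesis 3a.** "A change score will be computed between SPS score at baseline and after 4 weeks for each subject". The arms are compared by two-sample t-test, and Y-BOCS and YGTSS change is handled likewise. Baseline scores enter the model only if the arms differ at baseline.
- **Section 2.2.** Entry requires an SPS score of at least 6.

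I read baseline in section 4.2 as the Day 0 rating. Nothing in the efficacy analysis uses the Screening rating.

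**The concern.** A single interviewer rating carries measurement error, and all of that error passes into a change score. The trial collects a second rating before dosing, and the analysis does not use it.

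Precision is scarce. Section 2.1.1 aims for 30 patients at each of two sites, so about 30 per arm if allocation is 1:1 (the ratio is not stated). Y-BOCS and YGTSS are given by diagnosis, so those comparisons have fewer than 30 per arm. Clinical symptoms are among the primary endpoints. The mediation tests for Hypotheses 3b and 3c are run only if the SPS comparison is significant, so power lost in Hypothesis 3a also reduces the chance of reaching the mechanism questions.

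**Working it through.** The plan states no power, SD, effect size or correlation for these scales, so there is no figure to reproduce. The correlations below are assumptions.

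**Notation.** S, B and 4 are the Screening, Day 0 and week-4 ratings, with common variance 1 and correlations r_SB, r_B4 and r_S4.

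**Formulas**

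1. Planned change score (4 minus B): variance 2(1 − r_B4).
2. Change from the mean of S and B: variance 1 + (1 + r_SB)/2 − r_B4 − r_S4.
3. Week 4 adjusted for B only: residual variance 1 − r_B4².
4. Week 4 adjusted for both: residual variance 1 − (r_B4² + r_S4² − 2·r_B4·r_S4·r_SB)/(1 − r_SB²).

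**Worked example, all correlations 0.5.** (1) 2 × 0.5 = 1.00. (2) 1 + 0.75 − 1.00 = 0.75. (3) 1 − 0.25 = 0.75. (4) 1 − (0.25 + 0.25 − 0.25)/0.75 = 0.667.

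**Results**

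| r_SB, r_B4, r_S4 | Mean of two ÷ planned | Day 0 covariate ÷ planned | Both covariates ÷ planned | Both ÷ Day 0 alone |
|---|---|---|---|---|
| 0.3, 0.3, 0.3 | 0.75 | 0.65 | 0.62 | 0.95 |
| 0.5, 0.5, 0.5 | 0.75 | 0.75 | 0.67 | 0.89 |
| 0.7, 0.7, 0.7 | 0.75 | 0.85 | 0.71 | 0.83 |
| 0.71, 0.64, 0.61 | 0.84 | 0.82 | 0.75 | 0.92 |
| 0.60, 0.525, 0.45 | 0.87 | 0.76 | 0.73 | 0.96 |
| 0.80, 0.70, 0.65 | 0.92 | 0.85 | 0.81 | 0.96 |
| 0.75, 0.60, 0.50 | 0.97 | 0.80 | 0.79 | 0.99 |
| 0.80, 0.60, 0.50 | 1.00 | 0.80 | 0.80 | 1.00 |
| 0.85, 0.70, 0.60 | 1.04 | 0.85 | 0.85 | 1.00 |
| 0.90, 0.60, 0.50 | 1.06 | 0.80 | 0.79 | 0.99 |

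**Plain mean.** With equal correlations ρ the ratio is 1.5(1 − ρ)/[2(1 − ρ)] = 0.75 at every ρ. The SE ratio is √0.75 = 0.866, a 13% reduction. At 30 per arm and two-sided 0.05 (sidedness is not stated), an effect with 80.0% power on the planned change score would have Φ((1.960 + 0.842)/0.866 − 1.960) = 89.9% power. That is the equal-correlation case. Comparing formulas 1 and 2, the mean helps only if r_B4 − r_S4 < (1 − r_SB)/2. With r_SB = 0.9, the gain is gone once r_S4 is 0.05 below r_B4. In simulation, selecting on the Screening score with otherwise equal correlations gave a reduction of 26 to 30%, so 25% is not a strict ceiling.

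**Both covariates.** The ratio to the planned variance runs from 0.62 to 0.85 for r_B4 of 0.3 to 0.7. Day 0 alone already gives (1 + r_B4)/2, that is 0.65 to 0.85. The second rating then removes 0 to 17%. At equal correlations of 0.9 it would remove 22%.

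**Cost of estimating the covariates.** With n patients in total and k covariates, the expected variance of the adjusted difference is inflated by 1 + k/(n − k − 3). With n = 60 this is 57/56 for one covariate and 57/55 for two. The second covariate costs 56/55, or 1.8%. Both together cost 3.6%, so the least favourable row above becomes 0.85 × 1.036 = 0.88, still below 1.

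**The case against.** The strongest reply is that the plan contains no error. The last rating before dosing is the ordinary choice of baseline, and it gives an unbiased comparison. That stands.

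There are also good reasons not to redefine baseline as the mean of the two ratings:

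- The Day 0 rating is described as a check for change since Screening. A rating anchored on the earlier score shares its error, and averaging does not remove shared error.
- The two ratings are not exchangeable. Screening may be by video, while the Baseline and Final Visits are both at NKI. Eligibility is also selected on a pre-treatment SPS threshold. No interval between Screening and Day 0 is stated. These features make a weaker link between Screening and week 4 plausible, and there the gain from a mean shrinks or reverses.
- Hypothesis 3c pairs SPS change with change from the Day 0 scan. A mean that reaches back to Screening would make the two changes cover different intervals.

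These points defeat the plain mean. They do not defeat using the Screening rating as a covariate, because the regression sets its weight and Day 0 remains the baseline.

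A reader might infer that the plan throws away a quarter of its precision. The documents do not support that: the quarter needs equal correlations, which they do not give. A reader might also infer that regression to the mean distorts the result. The plan does not name Screening as the baseline, and entry selection acts on both arms alike, so the randomised comparison is not biased.

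**Conclusion.** The point holds as a modest, optional gain in efficiency. Each applicable scale has two ratings before dosing, and the Hypothesis 3a analysis uses one.

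The size rests on assumed correlations. For a plain mean, the change in variance runs from a 25% reduction to none, or a loss of about 4 to 6% in the least favourable cases tabulated; steeper decay would cost more. For both ratings as covariates, residual variance is about 0.62 to 0.85 of the planned value when r_B4 lies between 0.3 and 0.7. Most of that gain comes from always adjusting for Day 0. The part owed to the second rating is about 0 to 17%, before the 1.8% cost of estimating its coefficient. If symptoms drift quickly, or Day 0 is anchored on Screening, the second rating adds nearly nothing.

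**What to change.** Amend section 4.2, before unblinding, as follows:

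1. Name the Day 0 Baseline Visit rating as the baseline for change in SPS, Y-BOCS and YGTSS, and for the Hypothesis 3c mediation.
2. Compare arms on each week-4 score in a linear model with arm, the Day 0 rating and the Screening rating, in all cases and not only when the arms differ at baseline. With Day 0 in the model, the arm effect is the same whether the outcome is week 4 or change from Day 0, so it still estimates a difference in change.
3. State that this SPS test is the one that opens Hypotheses 3b and 3c.
4. Keep the planned t-test on change from Day 0 as a sensitivity analysis.
5. Leave the optional phone-screen SPS out, since not every patient will have it.
6. Confirm that full scale scores, and not only a note of changes, are recorded on Day 0.

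No new visits or data are needed if item 6 is met. The statistical cost of the second rating is one degree of freedom, under 2% of variance with 60 patients. It is more for Y-BOCS and YGTSS, which have fewer: with 30 patients in total, as an illustration, 26/25, or 4%. The change touches a primary endpoint in a trial already under way, and the DSMB reviews amendments, so it needs a dated amendment and not just an edit to the wording.

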1.2 Hypotheses

Aim 1 of the study (the R21 phase) has been completed. This application applies only to the R33 phase (Aim 2).

Aim 2 (R33): Further validate neural targets in a sample of OCD and TD patients with sensory phenomena. Employing a placebo-controlled parallel group design, we will measure the effects of 4 weeks of optimal dose ondansetron (that with the greatest effect on neural targets in the R21 phase: 24 mg) on activation and connectivity of insula and somatosensory cortex in patients with at least moderate SP (measured with the Sensory Phenomena Scale7). Hyp. 2: Compared to placebo, ondansetron will be associated with greater decreases in the activation and connectivity of insula and somatosensory cortex from baseline to week 4.

Aim 3 (R33): Examine the relationship between target engagement and clinical symptoms. Hyp. 3a: Compared to placebo, ondansetron will be associated with greater reductions of SP from baseline to week 4, Hyp. 3b: Decreases in overall symptom severity (measured with Y-BOCS and Yale Global Tic Severity Scale) from baseline to week 4 will be mediated by reductions in SP, Hyp. 3c: Decreases in SP between baseline and week 4 will be mediated by reduced activation and connectivity of insula and somatosensory cortex.

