2.1 Number, Gender, Age and Racial/Ethnic Origin of Subjects

2.1.1 Number

It is expected that approximately 45 participants will be enrolled at NYU Langone Medical Center in order to produce 30 eligible participants at this site. Approximately 45 participants will also be enrolled at Nathan Kline Institute to produce 30 evaluable participants at that site. Participants enrolled at NYU will primarily be recruited from flyers throughout the NYU campus, internet advertisements, newspaper advertisements, recruitment emails to university mailing lists and previous studies from prior studies conducted by the lab and will directly contact the Research Coordinator for more information.

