Participants will return to NKI to repeat MRI scanning (see Baseline Visit for procedures). In addition, they will fill out the same questionnaires as during the Baseline Visit and have their symptoms re-assessed with the Y-BOCS/YGTSS and SPS. Side effects will again be evaluated using the PRISE. Suicidal ideation will be assessed using the QIDS item # 12. Repeat EKG and Bloodwork will be performed at the NKI Outpatient Research Department (OPRD; Director: [name], co-investigator on the approved IRB protocol at the NKI site) and the subject will meet with a study team physician. The Final Visit will ideally be scheduled for Day 28; realistically, we will allow patients to come into the lab within a window of +/- 7 days.

In the rare instance that the patient wishes to break up the final visit, which is long, into two shorter appointments (scanning one day and medical testing on another day), we will try to accommodate their schedule. If the patient is from the NYC area and will be transported up to NKI via car service provided by the study, the repeat EKG and bloodwork and physician appointment may occur at the Bellevue CTSI instead of at the NKI OPRD.

At the end of the Final Visit, subjects will be provided with psychiatric referral if desired. Arrangements will be made to compensate subjects for their time.

Total time for participation, including the Screening Visit, Baseline Visit, Mid-Trial Visit and the Final Visit, and the 2 phone calls will be approximately 16-20 hours.

Approximately one week after the Final Visit, the study coordinator will make a follow-up phone call with the patient to ask how they are functioning after completing the study and provide referral if necessary.

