4.2 Data Analysis and Data Monitoring

(See R21/R33 application for section references)

The primary endpoints of the study are clinical symptoms and fMRI data. The specific analyses (independent and dependent variables) will be unique to each task, as described below. Safety and tolerability of 4 weeks of 24 mg ondansetron will also be evaluated.

Alpha level will be set at 0.05 for all analyses. Task-based fMRI analysis will focus on brain activation in an a priori ROI consisting of bilateral insula and somatosensory cortex, although exploratory whole-brain analyses will also be conducted. Primary group-level analyses for the R33 phase will be performed on a modified intent to treat sample consisting of participants completing at least 2 weeks of treatment. Missing data values are expected to amount to 10% or less of the data. We will consider them as MAR and impute based on a regression model. The degrees of freedom of t-tests will be adjusted appropriately. Secondary per-protocol analyses will also be conducted.

Task-based and symptoms analyses for R33:

First-level fMRI analysis: For each fMRI task, image analysis at the first (subject) level will specify separate regressors for baseline and week 4 for conditions of interest (e.g., for the "urges-for-action" task: blink suppression at baseline, blink suppression at week 4, rest at baseline, rest at week 4) to examine contrasts between baseline and week 4 (e.g., blink suppression vs. rest for baseline vs. week 4). For each task, contrasts will also examine activation during the baseline scan only (e.g., blink suppression vs. rest at baseline scan). These latter contrasts will be performed in order to measure and adjust for any baseline differences in ROI activation between ondansetron and placebo groups.

Group-level fMRI analysis: Testing for Hypothesis 2: Two-sample t-tests will compare ondansetron and placebo groups on change in activation over the 4-week trial (using first-level contrasts comparing baseline with week 4). However, if there are significant baseline differences between the groups within the insula and somatosensory ROI (using two-sample t-tests on baseline scan contrasts), standardized parameter estimates will be extracted from these regions for each subject. These parameter estimates will then be specified as covariates in follow-up one-way ANOVAs comparing ondansetron and placebo groups on change in activation from baseline to week 4 after adjusting for baseline differences.

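### Hypotheses 3b and 3c get an indirect-effect estimate only if two group comparisons are significant, so this part of Aim 3 can end without one

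*Combined protocol and SAP*

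**What the plan says.** Section 1.2 sets Aim 3 as "Examine the relationship between target engagement and clinical symptoms". It states both mediation hypotheses without any condition. Under 3b, decreases in overall severity "from baseline to week 4 will be mediated by reductions in SP". Under 3c, the SP decreases are mediated by reduced activation and connectivity of the target regions.

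Section 4.2 then makes the analyses conditional. For 3b, a Sobel test follows only "If there are significant differences between ondansetron and placebo groups in (1) SPS change scores and (2) Y-BOCS or YGTSS change scores". For 3c, it follows only if the groups differ significantly in SPS change and in ROI activation or connectivity change; then "a Sobel test will investigate whether group differences in SPS change are mediated by changes in activation or connectivity". SPS change is in both conditions, so a non-significant result for Hypothesis 3a removes both analyses.

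Two parts of section 4.2 bear on Aim 3 and are unconditional: the group comparisons of SPS, Y-BOCS and YGTSS change, and the exploratory correlations of SPS with whole-brain activation and connectivity. Neither estimates an indirect effect. Section 4.2 also adjusts for clinical and demographic differences left between the arms, but it does not state the mediator-outcome confounding assumption that a mediation analysis needs.

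**The concern.** A mediation hypothesis asks how much of a treatment effect passes through the mediator. Here that quantity is computed only in trials where two t-tests both reach 0.05. Otherwise the report has neither an estimate nor an interval, and a reader cannot tell a small indirect effect from an imprecise one. When both tests pass, the arm-to-mediator path has been selected for being large, so the product of paths tends to be too large as well. With about 60 patients, either outcome is plausible.

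**Working it through.** **Inputs from the documents.** Section 2.1.1 plans about 45 enrolled per site for 30 usable participants each; for the second site it says "to produce 30 evaluable participants at that site". The total is 30 + 30 = 60. Section 4.2 sets alpha at 0.05 and uses two-sample t-tests on change scores. No power calculation, effect size or SD is given, so there is no stated figure to reproduce.

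**Assumptions.** Allocation 1:1 (30 per arm), two-sided tests, within-arm SD of 1. SPS effect a = 0.74 SD, which one t-test detects with about 80% power at 30 per arm; 0.5 and 1.0 SD are also run. Slope b = 0.3, 0.5, 0.7. Direct effect c′ = 0 (full mediation) or 0.4 SD. For the main table, all 60 patients are on one severity scale.

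**Model.** Mediator change M = a·arm + e1. Outcome change Y = b·M + c′·arm + e2. Indirect effect = a·b; total effect = a·b + c′. Power of one test comes from the noncentral t with 58 df and noncentrality d·√(30/2). The condition is met when both t-tests have p < 0.05.

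**Step 1: 3b at a = 0.74 (6,000 simulated trials per setting).**

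| | b = 0.3 | b = 0.5 | b = 0.7 |
|---|---|---|---|
| **c′ = 0:** total effect (SD) | 0.222 | 0.370 | 0.518 |
| Power, outcome comparison | 13.5% | 29% | 50.5% |
| Both comparisons significant | 12.6% | 27.8% | 48.5% |
| No estimate | 87% | 72% | 52% |
| Mean reported estimate / truth | 0.257/0.222 = 1.16 | 0.440/0.370 = 1.19 | 0.624/0.518 = 1.20 |
| **c′ = 0.4:** total effect (SD) | 0.622 | 0.770 | 0.918 |
| Power, outcome comparison | 66% | 83.5% | 94% |
| Both comparisons significant | 57.1% | 70.9% | 78.2% |
| No estimate | 43% | 29% | 22% |
| Mean reported estimate / truth | 0.253/0.222 = 1.14 | 0.416/0.370 = 1.12 | 0.583/0.518 = 1.13 |

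Repeat runs move these figures by about one percentage point, which gives the ranges 52 to 88%, 21 to 43% and 12 to 21%. Section 4.1 says "OC symptoms in OCD patients will be assessed using the Yale-Brown Obsessive Compulsive Scale", with the YGTSS for tic patients, so each scale may cover only part of the 60. With a 30/30 split and the plan's either-scale rule, the condition is met about as often: 15.7, 26.5, 45.2% (c′ = 0) and 52.3, 67.0, 77.1% (c′ = 0.4).

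**Step 2: which comparison fails.** Under full mediation the outcome comparison misses in 49.5 to 86.5% of trials, against about 20% for SPS, so the outcome dominates. With c′ = 0.4 and slopes 0.5 to 0.7, SPS fails in 67 to 93% of the trials without an estimate and the outcome in 28 to 58%.

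**Step 3: inflation at other effects.** At a = 0.5 the mean reported estimates are 0.214, 0.381, 0.532 (c′ = 0) and 0.214, 0.359, 0.498 (c′ = 0.4), against true values 0.150, 0.250, 0.350: ratios 1.42 to 1.52. At a = 1.0 they are 1.07 to 1.09 under full mediation, and 1.02 to 1.03 when both group differences are 1.0 SD. The cause is upward selection of the arm-to-mediator path: with both differences 0.5 SD and b = 0.5, it averages 0.74 against a true 0.50. If b = 0 and there is no confounding, reported estimates average zero. Estimated in every trial, the indirect effect averages the true value.

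**Step 4: 3c.** Taking one mediator value per patient and equal differences on SPS and the brain measure, no estimate results in 65 to 73% of trials at 0.5 SD, 20 to 24% at 0.8 SD and about 6% at 1.0 SD. The plan's choice between activation and connectivity would meet the condition more often; that is not modelled.

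**Step 5: confounding.** With no mediation (b = 0) and error correlation ρ, the unconditional estimate averages a·ρ: 0.74 × 0.3 = 0.222 SD and 0.74 × 0.5 = 0.37 SD. These equal the true effects at slopes 0.3 and 0.5 in Step 1.

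**The case against.** Requiring a group difference before testing mediation is common practice, and section 4.2 asks whether group differences are mediated, which presumes that they exist. That stands for a claim of mediation. It does not require withholding the estimate.

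Aim 3 is also not left empty when the condition fails. The group comparisons and the SPS-brain correlations are still reported, so a reader who inferred that the aim would yield nothing would go too far. What is lost is the size and uncertainty of the indirect effect.

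Step 5 is the strongest counterpoint: an unconditional estimate can reflect confounding alone. In 3b the concern is concrete, because at the final visit patients "have their symptoms re-assessed with the Y-BOCS/YGTSS and SPS", so mediator and outcome are rated together. A reader might infer that the condition wastes power that testing without it would recover. That does not follow. With no mediation and error correlation 0.3 or 0.5, an unconditional 95% interval excludes zero in about 50% or 80% of trials. The condition protects against such claims and should stay for them.

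A reader might also infer that 3b must be tied to one severity scale. Nothing in the documents requires that, and it is a trade-off: at a 30/30 split, slope 0.7 and full mediation, true claims would fall from 38 to 23% of trials, even with a Monte Carlo interval in place of Sobel.

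**Conclusion.** The point holds in a limited form. Section 4.2 makes the only planned indirect-effect analyses depend on two significant comparisons and offers no fallback estimate or interval. Under the stated assumptions, the chance of no 3b estimate at an SPS effect of 0.74 SD is about 52 to 88% with full mediation and 21 to 43% with a 0.4 SD direct effect. Inflation of reported estimates is moderate at that effect (about 12 to 21%), larger at 0.5 SD (roughly 40 to 50%) and small at 1.0 SD (2 to 10%).

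It would be too strong to say that every reported estimate will be materially too high, or that one comparison is always the bottleneck. The documents give no effect sizes that would settle either, and both vary across the range. The trial's main comparisons are unaffected. This is a change to consider, not a defect that undermines the trial.

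**What to change.** In section 4.2, replace the two conditional Sobel sentences with text to this effect:

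> For Hypothesis 3b (each severity scale, in the patients rated on it) and Hypothesis 3c (one mediator value per patient), the indirect effect and its 95% Monte Carlo or bootstrap interval will be estimated from two regressions: arm to mediator change, and arm plus mediator change to outcome change, with baseline values as covariates. It will be reported as a secondary estimate whether or not the group comparisons are significant. Mediation will be claimed only if both group differences are also significant. The estimate assumes no unmeasured mediator-outcome confounding. An interval that includes zero is not evidence of no mediation.

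For 3c, the mediator could be the mean task contrast over "an a priori ROI consisting of bilateral insula and somatosensory cortex". A whole-brain connectivity map from a seed does not by itself give one value per patient.

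**Cost.** Wording and a few lines of code; no new data or visits. Intervals will be wide: median width 0.50 to 0.77 SD with 60 patients on a scale and 0.77 to 1.12 SD with 30, simulated without baseline covariates. The estimate is sensitive to confounding (Step 5), so it must carry that caveat and not support a claim alone. If the interval replaces Sobel as the test behind a claim, false claims at error correlations 0.3 and 0.5 with a 0.4 SD direct effect rise from about 12 and 28% to 17 and 31%, with 60 on one scale; keeping Sobel for claims avoids this.
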